### **3.15 RISK**

Compared to the traditional implantation method of implanting miniscrews in treatment, this experiment will produce 3D guide. Therefore, it is possible to increase the cost of planting nails

### **3.16 Sensitivity and interests of the community**

**Understand and respect the culture, values, and habits of the target community.**  
**Ensure that the research design and implementation process respects these cultural characteristic**

### **3.17 Ethical review**

### **3.18 Compensation**

**During the treatment process, complications may occur, such as infection at site of miniscrew insertion, miniscrew loose and dislodge, and also injury to the**

tooth roots. If the above situation occurs, Department of Stomatology, Xuanwu Hospital of Traditional Chinese Medicine will bear all the treatment costs of the patient.

### **3.19 Possible benefit**

This study will benefit individuals where the process of miniscrew implantation is likely to be safer if patients receive Intervention treatment during miniscrew implantation. Participants will have material fees waived as a reward.

## **Chapter 4**

### **DUMMY TABLES**

#### **4.1 Annexure A**

**To compare the accuracy of TADs.**

Name: \_\_\_\_\_

Ref. No. \_\_\_\_\_

**The linear deviation of the TADs.**

Miniscrew at BP		Miniscrew at MD		Miniscrew at VD	
Miniscrew Cap	Miniscrew Tip	Miniscrew Cap	Miniscrew Tip	Miniscrew Cap	Miniscrew Tip

BP, bucco-palatal direction; MD, mesio-distal direction; VD, vertical direction.

#### **The angle deviation of the TADs.**

Miniscrew at BP		Miniscrew at MD		Miniscrew at VD	
Right side	left side	right side	left side	right side	left side

#### **4.2 Annexure B**

#### **To compare the safety of TADs.**

Name: \_\_\_\_\_

Ref. No. \_\_\_\_\_

#### **the distance between miniscrew and the tooth root**

Intervention / Control groups		
Distance x axis	Distance Y axis	Distance Z axis

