**Blinding:**

The study will employ a particular-blind design to minimize bias. The participants and the researchers administering the interventions will be aware of the group assignments. And the researchers who interact with participants and collect data will be unaware of group assignments. This blinding helps to prevent expectations or biases from influencing the outcomes and ensures that the study results are more reliable.

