#### 4.3 Annexure C

**To compare the stability of TADs.**

Name: \_\_\_\_\_

Ref. No. \_\_\_\_\_

Date: \_\_\_\_\_

Months	1	2	3	4	5	6	7
Intervention group							
Control group							

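### Annexure C records monthly stability only in arm-named rows, which conflicts with the promised blinding of data collectors if the sheet is used as printed; Annexure B has a weaker form of the same problem

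*Protocol*

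**What the plan says.** Under Blinding, section 3.6 of the protocol divides the people involved into two sets. On one side, "The participants and the researchers administering the interventions will be aware of the group assignments". On the other, "the researchers who interact with participants and collect data will be unaware of group assignments". The stated purpose of the second provision is to keep expectations from influencing the outcomes.

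Chapter 4, titled as dummy tables, holds three annexures:

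- **Annexure A (4.1, accuracy)** has name and reference-number fields, then cells for linear and angular deviation. It shows no arm.
- **Annexure B (4.2)**, headed "To compare the safety of TADs", has name and reference-number fields. Its root-distance table prints "Intervention / Control" above the three axis cells.
- **Annexure C (4.3)**, headed "To compare the stability of TADs", has name, reference-number and date fields. Its table has month columns 1 to 7 and two rows, "Intervention group" and "Control group".

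Section 3.13 lists mobility of the miniscrew among the main efficacy indicators, assessed by clinical examination, and defines stability as looseness. It counts the distance from root to screw as a safety measure. Section 3.14 assigns image superimposition and measurement to two doctors and does not say whether they are blinded.

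**The concern.** Patients and operators know the allocation, so blinding the people who collect the data is the only masking the protocol offers. A sheet that asks the recorder to choose between two arm-named rows undoes that masking at the moment of recording. Anyone who opens the same sheet at a later month also sees the arm and the earlier results.

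This matters most for mobility, where the examiner decides whether a screw counts as loose. With 12 patients per arm (section 3.10), one changed call moves that arm's looseness proportion by 1/12, or about 8 percentage points. That shows how sensitive the stability comparison is to a single judgement. It is not an estimate of bias.

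**Working it through.** The protocol gives no figure to reproduce. The check sets the blinding text beside the three annexures.

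| Annexure | Outcome | Patient identifiers | Where the arm appears | Can it be completed without knowing the arm? |
|---|---|---|---|---|
| A (4.1) | Accuracy | Name, reference number | Nowhere | Yes |
| B (4.2) | Root distance (safety) | Name, reference number | A choice printed above the cells | Yes, if the choice is left unmarked |
| C (4.3) | Monthly stability | Name, reference number, date | As the only two row labels | No, as printed |

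1. **Are these recording sheets or result shells?** The chapter title points to shells. The name and reference-number fields, and the date on Annexure C, point to one sheet per patient, because a summary table by arm has no use for them. The protocol shows no other recording form. Patient-level sheets are the more natural reading, but the protocol does not say so.

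2. **Annexure C.** If it is a patient sheet, a monthly result can go only in the row of that patient's arm, so the recorder must know the allocation. Mobility is found by examining the patient, so whoever records it falls within those who "the researchers who interact with participants and collect data will be unaware of group assignments" describes. The conflict is direct.

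3. **Annexure B.** The three distances can be entered with the arm choice unmarked and the arm added later. Section 3.9.2.3 lists distance to the root among the CBCT variables, so these values are probably read from images by the two doctors of section 3.14. The blinding sentence covers researchers who both interact with participants and collect data. Whether image readers belong to that group is not stated. The sheet invites disclosure of the arm but does not require it.

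4. **Is the arm needed on the sheet?** Annexure A has the same name and reference-number fields and no arm label. Allocation can be linked later through the reference number. The protocol describes no coded form, no separate entry of the arm and no later step at which allocation is merged.

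**The case against.** The strongest reply is that Chapter 4 holds result shells. Annexure C puts both arms on one sheet under a heading about comparison, and no single patient could fill both rows. The protocol does not say who completes the annexures, when, or whether they are the source record at the examination. This stands in part: it makes the conflict conditional. It does not remove it, because on that reading the patient identifiers are out of place and the layout still needs correcting.

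The points about Annexure B also stand: it can be completed without marking the arm, and the image readers may lie outside the blinding sentence. A reader might infer that the blind is lost for both stability and safety. The documents support that for stability as recorded on Annexure C, not for root distance.

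A reader might also infer that any bias would favour the guide. Section 3.19 does expect implantation with it to be safer, and section 2.2.1 is favourable. But the hypotheses in section 1.11.4 are non-directional, section 2.2.2 lists disadvantages, and Table 2.2 includes a study that found both insertion methods safe and accurate. The direction cannot be fixed from this text.

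Finally, the blinding paragraph has a broader weakness: it does not name who examines mobility or say whether image readers are masked. Redrafting the sheets does not settle that.

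**Conclusion.** The point holds in a limited, conditional form. If Annexure C is used as printed to record mobility, it is incompatible with the blinding of data collectors in section 3.6. Annexure B has a weaker version of the same fault, since its arm field is unnecessary but can be left blank. The conclusion rests on reading the annexures as patient-level sheets, which the identifiers support and the chapter title does not.

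Its extent is structural: every one of the 24 planned patients would have stability recorded on a sheet that shows the arm. It is tempting to count cells, for example 24 × 7 = 168 monthly stability entries. That count is not secure. Sections 3.10 and 3.11 describe about 6 months of follow-up, which gives 24 × 6 = 144. Either figure assumes one screw per patient and no drop-out, although Annexure A has right and left columns and the sample size allows 20% drop-out. Neither count measures bias, and the size of any bias cannot be derived from the documents.

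**What to change.** - **Annexure C:** replace the two arm rows with a single patient row.
- **Annexure B:** delete the arm field above the distance cells.
- **Both sheets:** identify the patient by reference number only, as a coded form without name or arm.
- **Allocation key:** have it held by someone who does not assess outcomes, and merge it only after the measurements are locked.
- **Summary shells by arm:** if these are wanted, keep them separate and without patient identifiers.

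One added sentence in the protocol should say which annexures are recording forms, who completes them, and whether the two image readers are blinded.

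The cost is redrafting two templates and adding that sentence; no extra visits, procedures or staff are needed. The change removes the unblinding built into the sheets. Patients who know their arm could still disclose it to the examiner.

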#### 4.3 Annexure C

**To compare the stability of TADs.**

Name: \_\_\_\_\_

Ref. No. \_\_\_\_\_

Date: \_\_\_\_\_

Months	1	2	3	4	5	6	7
Intervention group							
Control group							

#### 4.4 Gantt chart for research activities

Research Activities	2024		2025		2026	
	Jan – Jun	Jul – Dec	Jan- Jun	Jul- Dec	Jan- Jun	Jul- Dec
Ethical application and approval from USM						
Data collection						
Data analysis and interpretation						
Thesis write-up and submission						

#### 4.5 Milestones and Dates

No.	Details	Estimated Date
1.	Ethical application and approval from USM	May 2024
2.	Data collection	January 2025
3.	Data analysis and interpretation	June 2025
4.	Thesis write-up and submission	January 2026

## **5. APPENDICES**
